10.6.2 Vital Signs

Vital signs and body temperature (measured orally) will be measured at Screening, all visits during the Treatment Period, and Follow-up Period visits. Vital signs, including systolic and diastolic blood pressure, radial pulse and respiration rate, will be measured after the subject has rested for at least 5 minutes in a supine or semi-supine position. Vital signs and body temperature will be monitored during IV infusion of the investigational product and periodically over the observation period after infusion. Additional vital sign measurements will be obtained at the discretion of the Investigator or designee if clinically significant signs or symptoms occur.

10.6.3 Electrocardiograms

A standard 12-lead ECG will be performed at Screening; during Induction Therapy (pre-dose and at the end of infusion) on Day 1 (Baseline, Week 0), Week 8, and Week 10 (refer to Table 9-1); during OLE therapy on Week 12 (pre-dose and at the end of infusion), Week 16 (pre-dose and at the end of infusion) (refer to Table 9-2); and at Week 52 of OLE/LTE Therapy (refer to Table 9-2). Subjects who transition from LTE to OLE must have ECGs performed pre-dose and at the end of infusion for the first two infusions. The ECGs will be recorded after the subject has rested for approximately 5 minutes in a supine position. When PK collections and ECG recordings are scheduled at the same time point, the ECG recording should be prior to the PK sample collection.

10.6.3.1 Investigative Site Responsibilities

The Investigator is responsible for evaluating the ECG interpretation in relationship to clinical signs and symptoms and reaching a medical decision regarding the subject's medical status. The ECG findings should be assessed by the Investigator as normal, abnormal not clinically significant, or abnormal clinically significant, as appropriate. All abnormalities, whether assessed as clinically significant or not, will be recorded. The ECG tracing should be initialed and dated by the Investigator.

10.6.3.2 ECG Core Laboratory Responsibilities

The use of a central ECG laboratory or central reader may be requested on an adhoc basis.

10.6.4 Physical Examination

The Investigator will perform complete physical examinations including general appearance and examination of head, eyes, ears, nose, and throat (HEENT) and body systems (cardiovascular, respiratory, abdominal, musculoskeletal, extremities, lymph nodes, and skin) at Screening, Baseline (Week 0, Day 1), End-of-Induction Therapy (Week 12), and End-of-OLE/LTE Therapy (Week 52). Brief physical examinations (only include HEENT, cardiovascular, respiratory, and abdominal examinations) will be performed at all other visits during the Treatment Period and Follow-up Periods as specified in Table 9-1 and Table 9-2.

Body weight (kg) and height (cm) will be obtained while the subject is wearing light clothing (without shoes). Body weight will be documented during the Screening visit and at each study visit during the Treatment Period and Follow-up Period; height will be recorded at the Screening visit only (refer to Table 9-1 and Table 9-2)

10.6.5 Adverse Events

10.6.5.1 Definitions

An AE is defined as any untoward medical occurrence in a clinical study subject administered an investigational product and does not necessarily have a causal relationship with the treatment. An AE can therefore be any unfavorable and/or unintended sign (e.g., an abnormal laboratory finding), symptom or disease temporally associated with the use of an investigational product whether or not considered related to the product.

An AE includes but is not limited to:

- Any clinically significant worsening of a pre-existing condition;
- An AE occurring from overdose (i.e., a dose higher than that prescribed by a healthcare professional for clinical reasons, or a dose higher than that described on the marketed product label) of an investigational or marketed product, whether accidental or intentional;
- An AE occurring from abuse (e.g., use for non-clinical reasons) of an investigational or marketed product.

The collection of AE and SAE information commences following the subject's written consent to participate in the study. The Investigator will inquire about AEs at all subject visits by asking the subject a non-leading question such as: "How have you been feeling since your last visit?" All AEs, whether observed by the Investigator or reported by the subject, must be collected. If a subject experiences an AE or SAE, the subject will receive appropriate treatment and supportive care as necessary, and the Investigator will continue to follow up

until there is a return to the subject's baseline condition, or until a clinically satisfactory resolution is achieved.

In addition to the Investigator's own description of the AEs, each AE will be coded by the Sponsor according to the Medical Dictionary for Regulatory Activities (MedDRA).

10.6.5.2 Assessment of Intensity

All AEs will be classified either as mild, moderate, or severe in intensity as defined below:

- **Mild** – Event results in mild or transient discomfort, not requiring intervention, or treatment; does not limit or interfere with daily activities (e.g., insomnia, mild headache).
- **Moderate** – Event is sufficiently discomforting so as to limit or interfere with daily activities; may require interventional treatment (e.g., fever requiring antipyretic medication).
- **Severe** – Event results in significant symptoms that prevents normal daily activities; requires interventional treatment and may require hospitalization or invasive intervention (e.g., anemia resulting in blood transfusion).

Refer to Section 7.5.3 regarding withholding investigational product administration if the subject experiences a severe AE not related or of unclear relationship to the investigational product; and discontinuing investigational product administration if the subject experiences a severe AE related to the investigation product.

The Investigator will be instructed to closely monitor each subject who experiences an AE (whether ascribed to the investigational product or not) until the outcome of the AE has been determined. The AE must be monitored until the return to the subject's baseline condition or until clinically satisfactory resolution is achieved (e.g., Grade 1 or stable).

10.6.5.3 Assessment of Relationship

The causal relationship of each AE to the investigational product (KHK4083 or placebo) must be determined by a medically qualified individual. The causal relationship should be assessed as one of the following:

Related

There is a reasonable causal relationship between the investigational product administration and the AE. The term "reasonable causal relationship" means there is evidence to suggest a causal relationship.

Not related

There is not a reasonable causal relationship between the investigational product administration and the AE.

10.6.5.4 Classifying Infusion Reactions

- **Mild** - infusion reaction requires no intervention and no interruption of the infusion; however, infusion interruption is permitted to observe the subject for resolution of any signs/symptoms before re-starting the infusion.
- **Moderate** - infusion reaction requires possible intervention (e.g., paracetamol orally and diphenhydramine 50 mg IV or an equivalent anti-histamine may be administered) and interruption of the infusion for at least 15 to 30 minutes prior to re-starting or discontinuing the infusion.
- **Severe** - infusion reaction requires medical intervention (i.e., immediate medical/nursing assessment and indicated supportive management per the institutional standard of care and local Investigator judgment until the signs/symptoms of the reaction have resolved) and immediate discontinuation of the infusion.

Refer to Section 8.1.3.3 for additional details on continuing or discontinuing investigational product administration following an acute infusion reaction.

10.6.6 Serious Adverse Events

An SAE is defined as any AE that:

- Results in death.
- Is immediately life threatening. The term “life threatening” as part of the definition of “serious” refers to an event in which the subject was at imminent risk of death without urgent intervention at the time of the event; it does not refer to an event that hypothetically might have caused death if it were more severe.
- Requires in-patient hospitalization or prolongation of existing hospitalization.
- Results in persistent or significant disability or incapacity or substantial disruption of the ability to conduct normal life functions.
- Is a congenital anomaly or birth defect.
- Is another important medical event. Important medical events are those that may not result in death, be life threatening, or require hospitalization, but may be considered an SAE when, based upon appropriate medical judgment, they may jeopardize the subject and may require medical intervention to prevent one of the outcomes listed above.

Examples of such medical events include allergic bronchospasm requiring intensive treatment in an emergency room or at home, or blood dyscrasias that does not result in in-patient hospitalization, or the development of drug dependency or drug abuse.

The term “severe” is often used to describe the intensity (severity) of a specific event (as in mild, moderate, or severe myocardial infarction); the event itself, however, may be of relatively minor medical significance (such as severe headache). This is not the same as “serious,” which is based on the outcome or action criteria usually associated with events that

pose a threat to life or functioning. Seriousness (not severity) serves as a guide for defining regulatory reporting obligations.

All AEs, whether non-serious or serious, must be recorded as appropriate. In addition, any AE that is initially considered serious or becomes serious must be reported as an SAE.

10.6.6.1 Notification of Institutional Review Board or Independent Ethics Committee of Serious Adverse Events

The Investigator must comply with the applicable regulatory requirements related to the reporting of SAEs to the IRB or IEC. The IRB/IEC must be informed in a timely manner by the Investigator of SAEs occurring at their investigative site during the study. Investigators must also submit safety information provided by the Sponsor to the IRB. Investigators (or the Sponsor accordingly to specified regulations) also must submit safety information to the IEC.

10.6.6.2 Adverse Event Contacts

All SAE reports and follow-up SAE documentation should be emailed to the Sponsor's Drug Safety Surveillance Department: [contact].

10.6.6.3 Urgent Safety Measures

In accordance with the principles of GCP as described in ICH E6, the Investigator(s) has/have primary responsibility for assuring subject safety throughout the performance of study procedures. An urgent safety measure is defined as any measure, which an Investigator may need to implement, which is a deviation from, or a change in, the protocol to eliminate an immediate hazard(s) to study subject(s) without prior IRB/IEC approval/favorable opinion.

The Investigator may take appropriate urgent safety measures in order to protect the subjects of a clinical study against any immediate hazards to their health or safety. However, the **Investigator must inform the Sponsor within 24 hours of having taken such measures.**

All dose-limiting toxicity reports, non-emergency inquiries, and general information regarding this study should be directed to the Clinical Trial Manager, or Medical Monitor. All urgent safety measures meeting the criteria for an SAE must be reported to the Sponsor within 24 hours of taking safety measures. Such reports can be initiated by telephone but must be officially documented by the Investigator by email ([contact]) and must include details of what measures were taken and the circumstances giving rise to those measures.

10.6.7 Adverse Event and Serious Adverse Event Reporting

The description of each AE will identify the subject, date of onset, the date of resolution, the severity of the event, the action taken regarding the AE and the investigational product (KHK4083 or placebo), the outcome of the event, and the relationship of the event to KHK4083 or placebo. A medical condition present at Screening, but that has increased in frequency or severity, must be recorded as an AE. For screen failures, SAEs should be collected and recorded only until the subject is determined to be a screen failure. Screening or withdraws consent to participate in the study, except for SAEs that occur outside of that window which are attributed to screening-specific procedures. All AEs with onset after signing of the ICF should be collected. Adverse events which occur prior to first administration of investigational product should be identified as occurring pretreatment. No AE data should be entered on the eCRF for screen failures.

Standard medical terminology should be used to document AEs. The subject's exact description of the event will be recorded in the source documentation. In the case of signs and symptoms, the underlying illness or diagnosis will be recorded as the event when known. For SAEs, a single term for the diagnosis or underlying illness should be provided on the SAE Report form; if the underlying illness/diagnosis is unknown, the chief sign/symptom making the event serious should be recorded. Suspected Unexpected Serious Adverse Reactions (SUSARs) will be collected and reported according to regulatory guidelines.

All serious and non-serious AEs must be followed for a final outcome until the end of the Post-treatment Follow-up Period. An outcome of "unknown" is not considered to be an acceptable final outcome. An outcome of "not resolved" is an acceptable final outcome for non-serious AEs at the end of a subject's participation in a study, and for SAEs at database lock.

All SAEs require expeditious handling to comply with regulatory requirements. **Any SAE occurring in a clinical study subject must be reported to the Sponsor or designee within 24 hours of the Investigator having knowledge of the SAE.**

The Investigator or other qualified individual at the investigative site must complete the SAE Report form and e-mail it to the Sponsor or designee. All telephone communication regarding an SAE must be followed by a written report.

The Investigator is obligated to immediately report to the Sponsor or designee any SAE occurring at any time after the subject signs the ICF and within 16 weeks after the last dose of investigational product, independent of the circumstances or suspected cause. In addition, the Investigator must promptly report to the Sponsor any SAE occurring at any other time after

completion of the study if a causal relationship to KHK4083 is suspected. For all SAEs, the Investigator is obligated to pursue and provide information as requested by the Sponsor in addition to that requested on the SAE Report form. Information must include a description of the AE in sufficient detail to allow for a complete medical assessment of the case and independent determination of causality. Supporting documentation such as hospital discharge summaries or appropriate laboratory reports should also be sent to the Sponsor. In the case of a subject death, a summary of available autopsy findings must be submitted as soon as possible to the Sponsor. The Investigator will ensure that information reported immediately by telephone or other means and information entered on the SAE Report form is accurate and consistent.

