12.5 Analyses of Safety Data

The overall safety and tolerability of KHK4083 compared to placebo administered in multiple IV doses will be determined for reported AEs (including SAEs), physical examinations, vital signs, body weight, 12-lead ECGs, and clinical laboratory tests. All summaries will be prepared for the Safety Analysis Set.

All subjects will be assessed from the signing of the ICF until 16 weeks after the last dose for potential AEs. Treatment-emergent adverse events (TEAEs) will be grouped and tabulated by MedDRA Preferred Terms (PT) and SOC. All TEAEs will be summarized showing the number and percentage of subjects for each event with a start time within the Treatment Period (i.e., Induction Therapy and OLE or LTE Therapy) and by cohort (KHK4083 versus placebo) during Induction Therapy or KHK4083 dose level versus placebo during OLE/LTE Therapy.

Secondary safety variables in each cohort (Induction Therapy) or KHK4083 dose level (LTE Therapy) will be:

- Serum chemistry, hematology, coagulation profile, and urinalysis parameters;
- Vital signs (systolic and diastolic blood pressure, radial pulse rate, and respiration rate);
- Incidence of abnormal 12-lead ECG findings.

Subject listings, summary tables, and figures including the change over time and shift tables will be generated for vital signs (including body temperature, systolic and diastolic blood pressure, radial pulse rate, and respiratory rate), 12-lead ECGs, body weight, and clinical laboratory assessments (serum chemistry, hematology, coagulation profile, and urinalysis). The results from physical examination will be presented in the subject data listings.

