8.1 Adverse events

The onset date of an adverse event will be compared to the date of investigational product dosing to determine if the adverse event is treatment-emergent or not. Adverse events with an onset date on or after the first date of investigational product dosing will be classified as treatment emergent adverse events (TEAEs). If the adverse event onset date is missing or partial, the date will be compared as far as possible with the date of investigational product dosing. Adverse events will be assumed to be TEAEs unless there is clear evidence (through comparison of partial dates) to suggest that the adverse event started prior to receiving the dose of investigational product.

TEAE will be summarized in a table that presents the number and percentage of subjects with any TEAE, with any serious TEAE, with any drug-related TEAE, with any TEAE leading to discontinuation and death overall and within each treatment period (Double-Blind Induction Therapy Period, LTE Therapy Period, and OLE Therapy Period) by treatments (each KHK4083 dose level versus placebo). It will also include the total number of adverse events in each of these categories. All TEAEs will be summarized showing the number and percentage of subjects for each event with a start time within the treatment period (i.e., Double-Blind Induction Therapy Period, LTE Therapy Period, and OLE Therapy Period) and by treatments (each KHK4083 dose level versus placebo) during Induction Therapy or KHK4083 dose level versus placebo during OLE /LTE Therapy Period. All TEAEs will be summarized by SOC and Preferred Term as well as by Preferred Term in decreasing frequency. Two additional summary tables are presented for serious TEAEs and Related TEAEs.

	Forms			
	Title	Statistical Analysis Plan Template		
	Code	Version	Effective Date	Page
	FRM_ST03_032	01	23 Apr 2015	35 of 53

Listings of all adverse events (including non-treatment-emergent events) will be provided. This listing will be presented by dose cohort and will include site-subject identifier, adverse event (SOC, Preferred Term, reported term), start date, stop date, study day, severity grade, seriousness, relationship to drug, action taken with study treatment, and outcome. Also SAEs will be listed in a similar format as described above. Deaths which are adverse events leading to death, adverse events leading to discontinuation and adverse events with withdrawal of investigational product also will be listed in the same manner.

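### TEAE status rests on onset date alone, so a pre-dose adverse event that worsens on treatment is missed if the site updates the existing record

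*Protocol*

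**What the plan says.** **What counts as an AE.** Protocol 10.6.5.1 includes "Any clinically significant worsening of a pre-existing condition" in the AE definition. Protocol 10.6.7 adds the recording instruction: "A medical condition present at Screening, but that has increased in frequency or severity, must be recorded as an AE". Protocol 10.6.6 requires an AE that turns serious to be reported as an SAE.

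**What each record holds.** Protocol 10.6.7: "The description of each AE will identify the subject, date of onset, the date of resolution, the severity of the event". AE collection begins at consent, and the same section says: "Adverse events which occur prior to first administration of investigational product should be identified as occurring pretreatment".

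**How events are classified.** SAP 8.1: "Adverse events with an onset date on or after the first date of investigational product dosing will be classified as treatment emergent". For missing or partial onset dates the default is treatment-emergent, but that test too asks only when the event started. Protocol 12.5 tabulates TEAEs as the "number and percentage of subjects for each event with a start time within the Treatment Period".

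**What is displayed.** The AE tables in SAP 9.4 (14.3.1-1.1 to 14.3.1-5.3) are all titled as treatment-emergent. So are Listings 16.2.7-2.1 to 16.2.7-2.5 in SAP 9.6, which cover all, serious, fatal, discontinuation and withdrawal events. Listing 16.2.7-1 holds pretreatment events. The text of SAP 8.1 also promises a listing of all AEs, including those that are not treatment-emergent.

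**The concern.** The collection rules and the analysis rule do not match. The protocol regards worsening as a reportable event; the TEAE rule looks only at when an event began. Screening can last 28 days and includes sigmoidoscopy with biopsy, so there is a real window in which an AE can start after consent and still be present at the first infusion. If that AE becomes severe or serious after dosing, the deterioration is what a TEAE table should show, yet a rule based only on onset date can leave it out.

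Safety and tolerability is the Part A primary objective, and dose groups are small, so one subject shifts a reported incidence visibly. About 40 sites are planned. If recording practice differs between them, the same clinical course would be counted at one site and not at another.

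**Working it through.** The plan gives no figure on this point to reproduce. The check is to follow three courses through the recording rules (protocol 10.6.1, 10.6.5.1, 10.6.6, 10.6.7) and then the classification rules (SAP 8.1, protocol 12.5).

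1. **A condition or abnormal laboratory value found at Screening worsens after the first infusion.** Protocol 10.6.1 sends clinically important abnormal Screening laboratory values to medical history. Protocol 10.6.7 requires the worsening of a condition present at Screening to be recorded as an AE, and that record has its own onset. Dated at the worsening, it meets SAP 8.1 and is a TEAE. Nothing is lost.

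2. **An AE starts between consent and first infusion, worsens on treatment, and the site opens a new record.** The basis is the worsening wording in 10.6.5.1. The new record has an on-treatment onset and is a TEAE. Nothing is lost.

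3. **The same AE, but the site changes severity or seriousness on the existing record.** Onset stays before the first infusion and the event stays flagged as pretreatment. It fails SAP 8.1 and does not start within the Treatment Period under protocol 12.5. It is therefore absent from the overall, SOC/preferred-term, relationship, maximum-severity, serious and discontinuation TEAE tables. It is also absent from Listings 16.2.7-2.1 to 16.2.7-2.5. It remains in Listing 16.2.7-1, in the all-AE listing promised in SAP 8.1 and, if serious, in SAE reporting. SAP 9.6 names no serious-event listing beyond the treatment-emergent one.

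Courses 2 and 3 are the same clinical event. The documents do not say which recording practice applies, and the eCRF and any completion guide are not among them.

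**Between periods.** An AE that starts in Induction is already a TEAE. If it worsens after the first extension dose and the record is updated, assignment by start time keeps it in Induction, and the extension tables do not show the worsening.

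**Weight of one affected subject.** Protocol 8.1.4.1 gives 9 KHK4083 subjects per Part A cohort and 18 in Cohort 4.
- Part A dose group: 1/9 = 11.1 percentage points.
- Recommended dose, both parts combined: 9 + 18 = 27, and 1/27 = 3.7 percentage points.

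**The case against.** The best defence is that the protocol already supplies the safeguard. Worsening of a pre-existing condition is an AE in its own right (10.6.5.1, with no restriction to Screening), and 10.6.7 orders it to be recorded. Protocol 9.1 defines Screening as Day -28 to Day -1, so an AE that begins in that window can be read as a condition present at Screening. Read this way, each worsening gets its own record with an on-treatment onset and is counted.

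This has force, and it rules out the stronger inference that such an event drops out of every TEAE table in all cases. It does not close the gap. Section 10.6.7 also has pre-dose AEs flagged as pretreatment and followed to a final outcome, which invites updating one record, and it never says that worsening of an already recorded AE starts a new one.

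Three further inferences should be resisted:

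- **That the rule decides the dose.** Escalation and dose selection rest on the Safety Monitoring Committee's review of cumulative safety data (protocol 6.3, 8.1.4.1). The unblinded Week 12 tables follow completion of Part B (SAP 4.5). SAE reporting within 24 hours, and the stopping criterion for severe related AEs in protocol 7.5.3, do not depend on TEAE status.
- **That the information is lost.** The event is still listed, primary reasons for discontinuation are tabulated separately (SAP 5.1), and laboratory and QTcF shift tables (SAP 8.2, 8.4) capture those kinds of deterioration independently. What is exposed is the AE summary counts and the TEAE-restricted listings.
- **That open-label worsening is credited to a placebo column because of this rule.** Note 3 to SAP Table 2 keeps placebo-randomised subjects under a Placebo label throughout the OLE. Dating the worsening changes the period in which it is shown, not that label.

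**Conclusion.** The point holds in conditional form. TEAE status depends on onset date alone in both documents, although the protocol treats worsening as an AE. Where a site updates an existing pre-dose record, severe or serious deterioration on treatment is left out of the TEAE tables and the TEAE-restricted serious, death and discontinuation listings. Where the site opens a new record, it is counted.

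The number of affected events cannot be derived from the documents; only the weight of each is known, as worked out above. A reader might be tempted to supply rates. Suppose 5–15% of the 27 + 18 = 45 planned KHK4083 subjects have an AE from Screening still ongoing at first dose, and 10–30% of those worsen. The expected loss is then 45 × 0.05 × 0.10 = 0.2 to 45 × 0.15 × 0.30 = 2.0 subjects. The chance of at least one is 1 − (1 − 0.005)^45 = 20% to 1 − (1 − 0.045)^45 = 87%. Those rates have no source in the documents, and the calculation assumes that every worsening stays on the old record, which is exactly what is unknown. It is not a range for this trial; if worsening is always recorded anew, the loss is zero.

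The change is still worth making. It is cheap, and it makes the TEAE counts independent of how a site chooses to record worsening.

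**What to change.** - **SAP 8.1 and protocol 12.5:** define a TEAE as an AE with onset at or after the first infusion, or an AE with earlier onset that increases in severity or becomes serious after the first infusion.
- **Protocol 10.6.7 and the eCRF completion guide:** state that such worsening is entered as a new record dated at the worsening.
- **Period assignment:** allocate the event to Induction, LTE or OLE by that date.

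The cost is about one sentence in each document, minor extra data entry at sites, and TEAE rates that may be slightly higher.
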